6.5.1 Monitoring for potential harm

The unblinded statistician will continuously monitor the trial for early evidence of a higher infection rate of MITT HIV-1 infection in the vaccine group compared to the placebo group to ensure participant safety. The monitoring will start from the 10th infection onward

VE halved in first 7 months

N=1300:1300 placebo:vaccine group

^{4.2%} annual incidence in placebo group 10% annual dropout 5% missed vaccinations

(pooled over vaccine and placebo) and after each additional infection it is decided whether the stopping boundary has been reached [VE(0-24)<0%]. It will continue until the first analysis for non-efficacy is performed. The potential harm monitoring uses the one-sided exact binomial test resulting in a boundary that is determined via controlling the overall type I error rate across tests at 5%. Figure 6-3 shows for example that when 60 infections are counted, with 40 infections in the active vaccine arm, the boundary has been reached. In general, the null hypothesis will be rejected when the probability that the observed infections are from the vaccine arm is significantly larger than 50% (blue line in Figure 6-3). If the prespecified stopping boundary is reached, then the unblinded statisticians will immediately inform the DSMB. In addition, the DSMB chair will be updated on the accruing unblinded HIV-1 infection data after each confirmed MITT infection. This monitoring guideline is chosen to allow stopping for prudence as early as possible, maximizing participant safety.

[figure not shown]

Figure 6-3 Potential harm stopping boundary for the total number of HIV-1 infections in the active vaccine regimen versus placebo. Blue line is the potential harm stopping boundary, red line displays the case that all of the infections are in the vaccine arm.

6.5.2 Monitoring for non-efficacy

Non-efficacy will be followed by means of a double monitoring rule. These analyses will start when all participants have reached the Month 13 timepoint, and 60 MITT infections have occurred, then approximately every 6 months until the end of Stage 1. The boundary is hit when the VE 95% CI upper limit is <40% for both VE(0-24) and VE(7-24). Figure 6-4 shows the cumulative probability of hitting a non-efficacy bound in time. If the non-efficacy boundary is hit prior to reaching the end of Stage 1, the final analysis will be performed at the time the boundary is hit (prior to reaching the end of Stage 1) and the results will be reported. For participants that are already beyond 24 months of follow-up, no further follow-up will be required. For the other participants, a decision would be made, based on input from the OG, on whether to still follow them up until their month 24 visit. Stage 2 will not be started in this case.

[figure not shown]

Figure 6-4 Cumulative probability of hitting a potential harm or non-efficacy bound in time

Additionally, the DSMB will monitor the trial for non-efficacy with the aim to detect early on scenarios where the null hypothesis would not be rejected if the study were to continue to its end. At each DSMB meeting, conditional power calculations will be provided. These calculations will help in interpreting the projected treatment-arm-pooled infection totals. The conditional power is defined as the power for rejecting H0: $VE(0-24) \le 0\%$, setting VE(0-24) = 50%. The conditional power will be calculated given the actual enrollment, dropout, and treatment-arm-pooled HIV-1 incidence data from trial start through the time of the interim analysis and compared to a benchmark of 50% power.

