6.4 Accrual and sample size

6.4.1 Sample size calculation for proof of concept endpoints (vaccine efficacy of a prime-boost regimen to prevent HIV-1 infection)

A targeted total of 2,600 HIV-uninfected adult women will be recruited. Trial participants will be enrolled over a 14-month period approximately and randomized to a placebo or vaccine regimen (1:1 randomization). Participants will receive vaccinations at Months 0, 3, 6, and 12 and be followed for HIV infection for a period of at least 2 years (stage 1) after enrollment until the primary analysis at the end of stage 1 is performed (when the last subject reaches the month 24 visit). If H0: $VE(7-24) \le 0\%$ is rejected at the end of Stage 1, then the trial participants will continue blinded follow-up for at least 36 months (stage 2). If stage 2 does not occur, then all trial participants will be unblinded at the end of stage 1.

The trial is designed so that a 0.025-level Wald test has approximately 90% power in the PP population to reject the null hypothesis:

H0: $VE(7-24) \le 0\%$ versus the alternative hypothesis H1: VE(7-24) > 0% if the level of VE(7-24) is 50%.

The sample size calculations are based on the power of a 1-sided 0.025-level Wald test for comparing cumulative incidences of HIV-1 infection by the Month 24 visit between randomized groups, in the presence of the sequential monitoring described below. Power is computed by simulating a large number of efficacy trials under assumptions described below using the R package seqDesign [46,47],

The following assumptions are made for the sample size calculations:

- 10% annual dropout incidence in each of the study groups
- halved VE in the first 7 months after enrollment
- 14-month uniform accrual with halved accrual during the first 3 months
- visits approximately every 3months for HIV-1 diagnostic tests
- 4.2% annual HIV-1 incidence that is constant over time in the placebo group
- Sequential monitoring of vaccine efficacy for the following outcomes:
 - Potential harm [Conclude that VE(0-24)< 0% based on the one-sided exact binomial test of the proportion of infections assigned to the vaccine group]
 - Non-efficacy [Conclude that VE(7-24) < 40% based on a 2-sided 95% nominal confidence interval for VE(7-24) lying completely below 40%, and VE(0-24) < 40% based on a 2-sided 95% nominal confidence interval for VE(0-24) lying completely below 40%]

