### 10.3 Monitoring for Futility to Assess Vaccine Efficacy

The objective of monitoring the trial for futility to assess VE is to monitor progress toward the minimal needed target number of treatment arm-pooled HIV-1 primary endpoint infections by the end of Stage 1 in the MITT and PP cohorts. Four targets are monitored for:

1. the total number of MITT HIV-1 infections needed to achieve 80% power to detect  $VE(0-24) = 43\%$  (i.e.,  $VE(0-7) = 25\%$ ,  $VE(7-24) = 50\%$  and assuming a constant placebo incidence rate over time),
2. the total number of MITT HIV-1 infections needed to achieve 60% power to detect  $VE(0-24) = 43\%$  (i.e.,  $VE(0-7) = 25\%$ ,  $VE(7-24) = 50\%$  and assuming a constant placebo incidence rate over time),
3. the total number of PP HIV-1 infections needed to achieve 80% power to detect  $VE(7-24) = 50\%$ ,
4. the total number of PP HIV-1 infections needed to achieve 60% power to detect  $VE(7-24) = 50\%$ ,

each calculated based on trial simulations using the R `seqDesign` package. The target numbers in 1.–4. are 108, 65, 79, and 49, respectively. The rationale for considering the four targets is as follows: (i) if the trial cannot achieve 80% power to detect  $VE(7-24) = 50\%$  (targets 1. and 3.), considerations about enrollment modification or expansion are warranted, (ii) if the trial cannot achieve even 60% power to detect  $VE(7-24) = 50\%$  (targets 2. and 4.), considerations about completing the trial early for futility to assess VE are warranted, and (iii) the MITT cohort allows for greater precision of estimation of the number of infections by the end of Stage 1 (targets 1. and 2.), while the PP cohort is used in the primary VE analysis (targets 3. and 4.).

Two versions of the futility monitoring report will be generated. A report provided to the DSMB will be included in 6-monthly closed DSMB reports, starting in October 2018, and will report:

- (a) the estimated distribution of the total (i.e., treatment arm-pooled) number of HIV-1 infections in the MITT cohort by the end of Stage 1, with corresponding power to reject  $H_0 : VE(0-24) \leq 0\%$  using a 1-sided 0.025-level Wald test under the alternative hypothesis that  $VE(0-24) = 43\%$ ,
- (b) the estimated probability that the total number of HIV-1 infections in the MITT cohort by the end of Stage 1 is  $\geq 108$  (target 1) with 95% credible intervals,

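### Protocol 6.5.2 sets the DSMB's conditional power at VE(0-24) = 50%, but the design alternative, and SAP 10.3, put VE(0-24) at about 43%

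*Protocol*

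**What the plan says.** Protocol 6.5.2 adds conditional power to the confidence-interval rule for non-efficacy. It is the power to reject VE(0-24) ≤ 0%, "setting VE(0-24) = 50"%, given actual enrolment, dropout and arm-pooled incidence, and it is "compared to a benchmark of 50% power". Its stated role is interpretive: "These calculations will help in interpreting the projected treatment-arm-pooled infection totals".

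The design assumptions in Protocol 6.4.1 include "halved VE in the first 7 months after enrollment". With the design value VE(7-24) = 50%, VE is 25% up to Month 7.

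SAP 10.3 carries this through to the 0-24 window. Its first target is "the total number of MITT HIV-1 infections needed to achieve 80% power to detect" VE(0-24) = 43%, which it explains as 25% to Month 7 and 50% after, with constant placebo incidence. For the four targets (MITT at 80% and 60% power, then PP at 80% and 60% power), "The target numbers in 1.–4. are 108, 65, 79, and 49, respectively".

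Protocol 6.5.4 separately gives the DSMB conditional power for VE(7-24) with a true efficacy of 50% in the future data.

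**The concern.** For one null hypothesis and one time window, the Protocol assumes 50% and the SAP assumes 43%. Only 43% agrees with the effect on which the trial was sized. If efficacy is halved before Month 7, VE(0-24) = 50% would need VE(7-24) = 0.5 / (7/48 + 17/24) = 58.5%, which is not the design alternative.

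The purpose of this calculation is to show the DSMB when a trial that is short of infections could no longer be expected to reject the null. Too large an assumed effect works against that purpose: reported power is too high at every projected total, and shortfall is flagged only at a lower total. The DSMB could also be given two MITT power figures for the same projected total, one from 6.5.2 and one from SAP 10.3, with nothing to explain the gap.

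**Working it through.** **Inputs.** One-sided 0.025 test, 1:1 allocation, 1300 per arm, placebo incidence 4.2% per year and constant, dropout 10% per year, VE halved to Month 7 (Protocol 6.4.1). VE(0-24) = 50% and the 50% benchmark (Protocol 6.5.2). Targets of 108 and 65 MITT infections at VE(0-24) = 43% (SAP 10.3). MITT power of 91.58% (Protocol Table 6-4) and a median of 150 MITT infections (Protocol Table 6-5) at VE(7-24) = 50%.

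**Step 1. VE(0-24) under the design alternative.**
HR(0-24) = 7/24 × 0.75 + 17/24 × 0.50 = 0.573, so VE(0-24) = 42.7%. This rounds to the SAP's 43%.

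On the cumulative-incidence scale it is slightly lower. Cumulative incidence is 1 − exp(−0.084) = 0.0806 for placebo and 1 − exp(−(0.0315 × 7/12 + 0.021 × 17/12)) = 0.0470 for vaccine, so VE = 41.7%.

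**Step 2. Formulas.** For e total infections and hazard ratio h:
- Schoenfeld: power = Φ(√e × |ln h| / 2 − 1.96)
- Freedman: power = Φ(√e × (1 − h)/(1 + h) − 1.96)
- Wald: power = Φ(−ln h / √(1/e₁ + 1/e₀) − 1.96), with e₁ = e·h/(1 + h) and e₀ = e/(1 + h)

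**Step 3. Reproduce the plan's own figures.**
- 80% power at HR 0.570-0.573: Wald 108-110, Freedman 105-107, Schoenfeld 100-102 infections (SAP: 108).
- 60% power: Wald 68-69, Freedman 66-67, Schoenfeld 63-64 infections (SAP: 65).
- Expected MITT infections with exponential infection and dropout: 95.1 placebo + 55.9 vaccine = 151 (Table 6-5 median: 150).
- Power at 150 infections and VE 42.7%: 92.7% (Schoenfeld), 91.4% (Freedman), 90.7% (Wald). A simulation of the Nelson-Aalen Wald test (6000 trials, visits about every 3 months, no interim stopping) gives 90.5% (Table 6-4: 91.58%).

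The formulas therefore follow the plan's figures closely.

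**Step 4. The two settings compared** (Schoenfeld / Freedman / Wald, %).

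| Projected MITT infections | VE(0-24) = 42.7% | VE(0-24) = 50% | Overstatement, points |
|---|---|---|---|
| 36 | 38.6 / 37.0 / 36.3 | 54.8 / 51.6 / 50.0 | 14-16 |
| 54 | 53.5 / 51.4 / 50.4 | 72.1 / 68.8 / 67.0 | 17-19 |
| 60 | 57.8 / 55.7 / 54.6 | 76.6 / 73.3 / 71.6 | 17-19 |
| 65 | 61.2 / 59.1 / 58.0 | 79.8 / 76.7 / 75.0 | 17-19 |
| 108 | 82.5 / 80.6 / 79.5 | 95.0 / 93.4 / 92.4 | 13 |
| 150 | 92.7 / 91.4 / 90.7 | 98.9 / 98.3 / 97.9 | 6-7 |

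Worked example (Wald, 36 infections, h = 0.5): e₁ = 12 and e₀ = 24; √(1/12 + 1/24) = 0.3536; 0.6931/0.3536 = 1.96; power = Φ(0) = 50%.

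**Step 5. Infections needed to clear the 50% benchmark.** At VE 50%: 32 (Schoenfeld), 35 (Freedman), 36 (Wald). At VE 42.7%: 50, 53, 54. The difference is 18 infections under each formula.

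At 65 infections, which the SAP equates with 60% power, the 6.5.2 setting would report 75-80%.

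**The case against.** The case for leaving the text alone has real substance.

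- **The SAP governs the monitoring.** Protocol 6.5 leaves the details of the monitoring plan to the SAP. SAP 6 puts the section 10.3 report before the DSMB at its meetings. That report uses 43% for the MITT cohort and 50% for VE(7-24) in the PP cohort. It contains no calculation at VE(0-24) = 50% and no 50% power benchmark. This stands, and it confines the defect to Protocol 6.5.2. However, the SAP does not withdraw the 6.5.2 calculation, and Protocol version 4.0 still promises it at each meeting.
- **The primary parameter is handled correctly.** The conditional power in Protocol 6.5.4 pairs VE(7-24) with 50%, as designed. This stands too. A reader might infer that all the power figures the DSMB sees are inflated; the documents do not support that.
- **No decision depends on it.** No stopping rule is tied to the benchmark, and the formal non-efficacy boundary rests on confidence intervals. This stands.
- **The benchmark result changes only at very low totals.** The two settings fall on opposite sides of 50% only for about 32-54 projected infections. That is below the SAP's target of 65 and far below the 1st percentile of 124 in Table 6-5. At 60 or more, both exceed 50%. This stands for the benchmark, but the reported power remains overstated above that range.
- **It may be a labelling slip.** Table 6-5 labels the halved-VE scenario simply 50%, and its MITT median of 150 fits 25%/50% (149 simulated) better than a constant 50% (142 simulated). If 6.5.2 follows that convention, nothing is overstated. But Table 6-5 has a footnote on the halving. Section 6.5.2 has none and names the 0-24 window in both the null and the alternative. A programmer would take it literally, and a slip would still need correcting.

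**Conclusion.** The inconsistency is real and the correction is small. Taken as written, Protocol 6.5.2 reports power for a larger effect than the design alternative: about 6-7 points too high at the expected 150 MITT infections and 17-19 points too high at 60-65. The 50% benchmark is cleared at about 32-36 projected infections instead of about 50-54.

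Two stronger readings are tempting and are not supported. The first is that the benchmark is passed too early. It is applied to power at a projected total and is not a milestone in time, so the accurate statement is that it is cleared at too low a projected total. The second is that a trial short of infections could go unnoticed. Any total at which the benchmark result changes is already below the SAP's 65-infection target, which is tracked in the reports to the DSMB and the Oversight Group.

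The figures rest on constant placebo incidence and on treating the projected infection total as fixed, since the documents give no interim data. The ranges reflect the choice among three standard approximations. The DSMB charter is not among the documents and may already settle the point.

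**What to change.** In Protocol 6.5.2, or in the DSMB charter, compute the conditional power for VE(0-24) under VE(0-7) = 25% and VE(7-24) = 50%, that is VE(0-24) = 43%, consistent with SAP 10.3. If the 50% was meant as VE(7-24), say so and state the halving explicitly, as Table 6-5 does.

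Also state whether the 50% power benchmark still applies beside the SAP 10.3 guidelines, which act on a probability below 25% of reaching 108 or 65 MITT infections.

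The cost is one number and one sentence. Sample size, stopping boundaries and the primary analysis do not change. The only downside is that the reported conditional power will look less favourable.

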6.5.3 Monitoring for high efficacy

The DSMB will also monitor for high vaccine efficacy (95% CI lower limit for VE [0-36] >70%). Interim analyses for high efficacy will begin following the first participant's 36 month visit (end of Stage 2), and will be performed together with those for non-efficacy monitoring. Stopping for high efficacy would entail study unblinding and offering placebo recipients vaccination. The criterion for continuing from Stage 1 to Stage 2 is given in Section 6.3.

Figure 6-5 shows the trial design. Whereas the timing of interim analyses is event-driven, the total number of Stage 1 infections is not fixed. The end of Stage 1 is when the last enrolled participant reaches the Month 24 visit. Ensuring all participants are followed to Month 24 maximizes power and precision for assessing VE(7-24).

[figure not shown]

Figure 6-5 Study design and stages. Triangles represent vaccination timepoints. Stage 1 is the calendar time since trial start until the last enrolled participant reaches the Month 24 visit. Stage 2 is the calendar time since the last enrolled participant reached the Month 24 visit until the last enrolled participant reaches the Month 36 visit. Participants who completed their Month 36 visit will be followed further with scheduled clinical visits until the end of the study (ie, when the last Month 36 visit is completed).

Early stopping of the study while Stage 1 is still ongoing will be recommended if the potential harm or non-efficacy boundary is met at a pre-specified analysis time, in which case the final analysis will be performed and Stage 2 will not occur. If none of the stopping boundaries are reached by the end of Stage 1, the primary endpoint of vaccine efficacy from Month 7 through Month 24 [VE(7-24)] is evaluated at the end of Stage 1. If the lower bound of the 2-sided 95% confidence interval for VE(7-24) is > 0% at the end of Stage 1 (equivalently, the 1-sided p-value for testing H0: VE(7-24) $\leq 0\%$ is below 0.025), trial participants will continue blinded follow-up through Stage 2. On the other hand, if at the Stage 1 efficacy analysis the lower bound of the 95% confidence interval for VE(7-24) $\leq 0\%$, Stage 2 will not occur even if none of the stopping boundaries were reached by the end of Stage 1.

6.5.4 Monitoring for futility to assess VE

The DSMB monitors the trial for futility to assess VE defined as overly slow progress toward the Target Number of Infections (defined below) or insufficient conditional power for the primary analysis given the observed data. This may occur if enrollment rates are too low and/or the incidence of HIV-1 infections is too low. The DSMB will monitor for futility to assess VE every 6 months starting no later than 12 months after the first participant is enrolled. All relevant data that are available regarding enrollment and dropout will be provided to the DSMB. Timings can be adapted at the discretion of the DSMB in case signs of futility to assess VE are seen. According to the design, enrollment is expected to take place within 14 months.

We define the Target Number of Infections to be the number of primary HIV-1 endpoints after Month 7 and by the Month 24 visit such that the trial has approximately 70% power to reject H0: $VE \le 0\%$ if VE = 50% (using a 1-sided 0.025-level cumulative hazard-based Wald test).

The DSMB will be provided with the distribution of infections together with the expected distribution of infections under the design assumptions (incidence, VE and dropout rates; table below). The conditional power for rejecting $VE(7-24) \le 0\%$ using the actual data, given a true vaccine efficacy of 50% in the future data, will also be provided to the DSMB at each interim analysis. More details on the data provided to the DSMB will be described in the DSMB charter.

Table 6-5 Probability distribution of all Stage 1 infections

VE*	Percentiles of distribution of number of Infections (Post Month 7)														
	1%	2.5%	5%	10%	20%	30%	40%	50%	60%	70%	80%	90%	95%	97.5%	99%
0%	105	110	112	116	120	123	126	128	131	134	138	143	148	151	154
50%	76	80	83	85	89	92	94	97	99	102	105	110	113	117	120
	Percentiles of distribution of number of Infections (MITT)														
0%	157	164	169	173	179	183	186	190	193	196	201	206	212	216	221
50%	124	128	131	136	141	144	147	150	153	156	160	166	171	174	179

*Halved in first 7 months

N=1300:1300 placebo:vaccine group

10% annual dropout

6.5.5 Monitoring for expanding enrollment

At the time of each DSMB meeting for which there are enough HIV infections to conduct an analysis, the HVTN 705/HPX2008 Oversight Group (OG) will receive the results of the operational futility analysis (which are blinded—pooled across treatment arms). The OG will also be provided additional information at the time of a special DSMB meeting scheduled to take place approximately 2 months before the completion of enrollment based on ongoing projections of time until full enrollment by study statisticians. For this meeting, study statisticians will prepare a report that includes the calculations typically in an operational futility analysis, along with additional guidance as to whether the HIV incidence – pooled over treatment arms—is "too low" or "acceptable" to sufficiently power the study. (The details of this guidance will be described in the study SAP.) The report will be shared both with the DSMB and with the study OG. The OG will then have the opportunity to decide whether, if incidence is lower than anticipated but not so low that operational futility is declared, to expand enrollment beyond the originally planned 2600, in order to maintain the ability of the study to meet the study's primary objectives. The meeting will be timed before but near to the end of enrollment, to allow a potential decision to expand enrollment to occur before the enrollment apparatus is scaled down, while also allowing the decision to be made on the maximal amount of primary endpoint infections. The OG will also be presented information on the degrees of enrollment expansion that would be required in order to achieve conditional power and treatmentarm-pooled infection totals at various levels.

6.5.6 Roles of study statisticians

HVTN SDMC statisticians will be "blinded" or "unblinded". Janssen statisticians will remain blinded until the primary analysis at Month 24. During protocol development and after primary follow-up is completed, there will be no distinction between the roles; both types of statisticians will be responsible for designing and analyzing the study. During the primary follow-up period, however, only the unblinded statisticians will see interim data broken down by treatment arm. Their role will be to conduct the interim monitoring and to produce and present reports on accruing data to the study DSMB. During the primary follow-up period, blinded statisticians will see only the interim data pooled across treatment arms. This way, blinded statisticians can assist protocol leadership in making decisions about modifications to the protocol without being influenced by interim efficacy results.

^{4.2%} annual incidence in placebo group

